2.3 Determination of Sample Size

A sufficient number of subjects will be screened to ensure the enrollment and completion of 84 subjects.

The number of subjects in this study is not based on statistical power considerations because the statistical analyses are primarily descriptive in nature. However, if at least 7 subjects complete each cohort, then there will be at least 65% to 85% probability of observing at least 1 occurrence of any AE with a true incidence rate for a given dose group of at least 15% to 25%, respectively.

It is estimated that dose escalation will occur for up to 3 dose levels (4 cohorts within each dose level). Each cohort will include 5 subjects randomized to active drug (SHP639) and 2 subjects randomized to placebo for an estimated total of at least 84 subjects.

For each cohort, the number of subjects will be increased as needed based on safety and IOP response to investigational product. Any cohort can be repeated to confirm findings with regard to safety or IOP response to investigational product.

2.4 Identification of Study Eye

For the purpose of overall analysis, 1 eye will be designated as the primary eye for the duration of the subject's participation in the study. In Cohort A single-dose treatment period (SDTP), the investigational product will be dosed in the designated study eye only. For all subjects participating in the multiple-dose treatment period (MDTP), a designated study eye will be also identified and the investigational product will be dosed in both eyes. For Cohort A, the study eye for MDTP will be the same as the study eye in SDTP. For SDTP Cohort A and MDTP Cohorts B, C and D, the following procedure will be used to determine the designated study eye:

- For each subject, the mean baseline IOP at a time point will be the mean of the IOPs on days -2 and -1 at that time point.
- The designated study eye will be the eye with the highest mean baseline IOP at the predose time point.
- If both eyes have equal mean baseline IOPs, the eye with the highest mean IOP at the +2-hour time point will be the designated study eye.
- If both eyes have equal mean IOPs at the +2-hour time point, the eye with the highest mean IOP at the +4-hour time point will be the designated study eye.
- If both eyes have equal mean IOPs at the +4-hour time point, the eye with the highest mean IOP at the +8-hour time point will be the designated study eye.
- If both eyes have equal mean IOPs at the +8-hour time point, the right eye will be the designated study eye.

3. OBJECTIVES

SHP639 is being developed for reduction of IOP in patients with ocular hypertension and primary open angle glaucoma. It is expected to act through a novel mode of action (natriuretic peptide receptor B agonism) that leads to an increase in trabecular meshwork outflow, thus reducing the IOP. SHP639-101 is a first-in-human clinical study for a topical ophthalmic formulation of SHP639. Up to 3 different SHP639 concentrations (0.1%, 0.3%, and 0.6%) will be explored and safety and tolerability of SHP639 ophthalmic solution will be evaluated. As a secondary objective, the study will also aim to characterize the pharmacodynamics (PD) of SHP639, using IOP as a PD biomarker. The pharmacokinetic (PK)-PD relationship will be explored if the data permit.

3.1 Study Objectives

3.1.1 Primary Objectives

The primary objective of this study is to investigate the safety and tolerability of single and multiple ascending concentrations of SHP639 ophthalmic solution in subjects with OHT or with POAG.

3.1.2 Secondary Objectives

The secondary objective of this study is to evaluate reduction of IOP, as a PD biomarker, following different SHP639 dosing regimens.

3.1.3 Exploratory Objectives

The exploratory objective for this study is to explore the PK-PD relationship of SHP639 in subjects with OHT or POAG.

4. SUBJECT POPULATION SETS

Each subject must participate in the informed consent process and provide written informed consent/assent before any procedures specified in the protocol are performed.

4.1 Enrolled Set

Enrolled set consists of all subjects who have signed informed consent.

4.2 Randomized Set

Randomized set consists of all subjects in the enrolled set for whom a randomization number has been assigned.

4.3 Safety Set

The safety set will consist of all subjects in the randomized set who had administered at least 1 dose of investigational product.

All safety analyses will be performed using the safety set. The placebo subjects will be pooled together as a pooled placebo group.

4.4 Pharmacokinetic Set

The pharmacokinetic (PK) set will consist of all subjects in the safety set for whom the primary PK data are considered sufficient and interpretable.

4.5 Pharmacodynamic Set

The pharmacodynamic (PD) set will consist of all subjects in the safety set for whom the primary PD data are evaluable.

5. SUBJECT DISPOSITION

Subject disposition will be summarized for the enrolled set. The disposition of subjects includes the number and percentage of subjects for the following categories: subjects who were enrolled, subjects who were randomized, subjects who were in the safety set, subjects who were in the pharmacokinetic set, subjects who were in the pharmacodynamic set, subjects who completed the study, subjects who prematurely discontinued the study treatment, and subjects who did not complete the study. Disposition data will be summarized by treatment group and overall by dosing regimen. All percentages will be based on the number of subjects randomized. Reasons for premature discontinuation from the study treatment period as recorded on the termination page of the eCRF will be summarized (number and percentage) by treatment group and overall by dosing regimen for the randomized set. The reason for study discontinuation may include any of the following: adverse event, withdrawal by subject, noncompliance with investigational product, physician decision, study terminated by sponsor, lost to follow-up, pregnancy, protocol deviation, trial screen failure and other. A by-subject listing of study completion information, including the reason for study discontinuation, where applicable, will be presented.

A listing of all Screen Failures (ie, subjects who were screened but not randomized) will be presented along with reasons for screen fail and details of any AEs.

6. PROTOCOL DEVIATIONS

A summary of the number and percentage of subjects in the randomized set with protocol deviations by treatment group and overall by dosing regimen will be produced.

All protocol deviation data will be listed for the subjects in the randomized set.

7. DEMOGRAPHIC AND OTHER BASELINE CHARACTERISTICS

Demographic variables such as age, sex, race, ethnicity, height, weight, and body mass index (BMI) at baseline will be summarized. Ocular assessments including Best Corrected Visual Acuity (BCVA) will be summarized separately for the study eye and non-study eye. Continuous variables, such as age (years), BMI, weight, height, and BCVA will be summarized using descriptive statistics for each treatment period, treatment group and overall by dosing regimen. Categorical variables such as sex, ethnicity, and race will be summarized by reporting the number and percentage of subjects in each category for each treatment group and overall by dosing regimen. Summaries will be performed using the randomized set.

Demographic data will be listed using the randomized set.

8. MEDICAL HISTORY

Medical history of subjects will be coded using the Medical Dictionary for Regulatory Activities (MedDRA) version 20.0. Recent ingestion of medication (received within 30 days or 5 half-lives (whichever is longer) before the date of the first dose of investigational product (see prior medications in section 10) and any ocular/non-ocular procedures performed within the 5 years before the date of the first dose of investigational product) and history of respiratory, cardiovascular, renal, gastrointestinal, hepatic, endocrine, hematological, neurological, psychiatric, and other diseases will be reviewed and recorded. The MedDRA version used for reporting the study will be documented in the summary table footnotes.

The number and percentage of subjects with medical history events in each primary system organ class (SOC) and each preferred term (PT) will be summarized by treatment group and overall by dosing regimen using the randomized set. Ocular history will be summarized for the study eye, the non-study eye, either eye if occurred in either eye, and both eyes if the event occurred in both eyes. Medical history will be counted for both eyes if a history with the same preferred term is present in both eyes regardless of the start date of history in each eye (e.g., the start date may differ between the two eyes.) Each subject's medical history will be listed by SOC and PT using the randomized set.

9. EXTENT OF EXPOSURE AND TREATMENT COMPLIANCE

9.1 Exposure to Investigational product

Exposure to double-masked investigational product for the Safety set will be summarized in terms of total number of drops, and treatment duration, which is calculated as the number of days from the date of first dose of double-masked investigational product taken to the date of the last dose of double-blind investigational product taken, inclusively for the MDTP. Descriptive statistics (n, mean, standard deviation, minimum, Q1, median, Q3, and maximum) will be presented by treatment group. Additionally, the number and percentage of subjects who had at least one dose of unrefrigerated drug will be summarized.

Exposure data including the number of doses received by each subject, and treatment duration will be presented in data listings. A separate exposure listing including only subjects receiving unrefrigerated drug will also be presented.

9.2 Measurement of Treatment Compliance

Treatment compliance will be calculated for MDTP only and will be calculated as:

Compliance (%) = (total actual dose administered / total expected dose) × 100;

Where,

1. If the subject completed the treatment: total expected dose = $x \times 27 + 1$ (the last dose was taken on the morning of Day 28)
2. If the subject discontinued the treatment, the date of treatment discontinuation will be used for date of expected last dose and total expected dose will be calculated as: total expected dose = $x \times (\text{date of expected last dose} - \text{date of first dose} + 1)$

Total actual dose = number of total doses taken between scheduled clinic visits + number of total drug instillations during all clinic visits,

Number of total doses taken between scheduled clinic visits is calculated as the

Sum of [$x \times (\text{the date of last dose prior to check-in at the current visit} - \text{date of last drug instillation from previous visit}) - \text{number of missed doses}$]

where $x = 1$ for Cohort A1, A2, and A3

$x = 2$ for Cohort B1, B2, and B3

$x = 3$ for Cohort C1, C2, and C3

$x = 4$ for Cohort D1, D2, and D3

Number of total drug instillations during all clinic visits is the sum of the numbers of drug instillation in all Study Drug Instillation CRFs of a subject.

The latest date of last dose prior to check in is the date found in Study Drug Accountability CRFs of a subject at each scheduled visit. If a subject has terminated the study early, the date of early termination on the Study Completion 1 CRF will be used. Number of missed doses is the numbers of missed doses in Study Drug Accountability CRFs of a subject at each visit. Descriptive statistics for investigational product compliance during the MDTP will be presented by treatment group for the Safety set. Individual subject compliance information will be listed with treatment group indicated.

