7.1.2 Treatment Period

Investigational product will be administered by study staff when subjects are present at the site during study visits.

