Subjects will be readmitted to the site on the evening of Day 26. Subjects will continue to receive their assigned doses, with the final dose being administered on the morning of Day 28. Subjects will undergo assessments and procedures as specified by visit in [Table 1](#) and by time point during each visit in [Table 2](#), [Table 3](#), [Table 4](#), and [Table 5](#), for Cohorts A, B, C, and D, respectively. They will be discharged from the site after completion of the morning assessments on Day 29.

Subjects who are prematurely discontinued from the study will complete the Day 29 assessments as fully as possible.

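### The SAP 9.2 compliance formula can score a fully adherent completer away from 100% when a day's doses are split between home and clinic

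*SAP*

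**What the plan says.** SAP 9.2 sets the scope first: "Treatment compliance will be calculated for MDTP only". For a completer the expected count is 27x + 1, because "the last dose was taken on the morning of Day 28", with x = 1, 2, 3 or 4 for Cohorts A, B, C and D.

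The actual count has two parts:

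- **Doses between visits.** For each interval, x is multiplied by the difference "the date of last dose prior to check-in at the current visit} - \text{date of last drug instillation from previous visit" (formula markup as extracted). Recorded missed doses are then subtracted. Both terms are calendar dates and carry no dose number within the day.
- **Doses at visits.** This count "is the sum of the numbers of drug instillation in all Study Drug Instillation CRFs of a subject".

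The protocol fixes part of where dosing happens. Section 7.1.2 says "Investigational product will be administered by study staff when subjects are present at the site during study visits". Table 1, footnote d, has subjects on site on Days 7, 14 and 21 from before the morning assessments until after the evening ones, and discharged once the Day 2 assessments are done. Section 7.1.2.2 makes subjects responsible for outpatient dosing on Days 3 to 26, and adds: "Subjects will be readmitted to the site on the evening of Day 26". Section 6.2.3.1 puts the first daily dose between 7 and 9 AM. The readable text does not say where the last dose of a visit day is taken.

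**The concern.** A date difference multiplied by x assigns whole days to home or clinic. It works only when all doses on each boundary day fall on one side of the visit. With two to four doses a day, a boundary day can be split, and SAP 9.2 has no rule for that.

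Two errors follow, in opposite directions. On Day 26, one dose at home before an evening check-in makes Day 26 the last home date, so all x doses of that day are credited; a later dose in the unit is added again as an instillation. On Days 7, 14 and 21, a dose taken at home after leaving falls in neither term, because the next interval starts from that same date.

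A reported percentage would then partly reflect where doses were taken. A double count can hide a missed dose, and an uncounted dose looks like non-adherence. The effect differs by regimen and possibly between the approximately 7 sites. With 5 active subjects per cohort (SAP 2.3), one adherent BID subject scored 94.5% lowers the active-group mean by (100 − 94.5)/5 = 1.1 points.

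**Working it through.** **Assumptions.** The subject completes treatment, takes every dose and has no recorded missed doses. Instillation forms count one instillation per dosing occasion, not one per eye. All on-site doses appear on those forms, including Day 27, when Protocol 3.1.4.2 and 3.1.5 describe dosing as self-administered.

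**Expected count (SAP 9.2).** 27x + 1 = 28 (QD), 55 (BID), 82 (TID), 109 (QID). This matches 27 full days plus one dose on the morning of Day 28.

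**Reference case: all doses on site on Days 1, 2, 7, 14, 21 and 27; all Day 26 doses at home.**

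- Home term: x[(6−2) + (13−7) + (20−14) + (26−21)] = 21x
- Clinic term: 6x + 1
- Total: 27x + 1, which is exactly 100% in every regimen

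**Departures from the reference case.** A last Day 26 dose given in the unit adds 1. Each visit day whose last dose is taken at home after leaving subtracts 1. Neither applies to QD, which has one morning dose.

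| Where doses were taken (all taken) | QD | BID | TID | QID |
|---|---|---|---|---|
| Reference case | 28/28 = 100% | 55/55 = 100% | 82/82 = 100% | 109/109 = 100% |
| Last Day 26 dose in unit (+1) | 28/28 = 100% | 56/55 = 101.8% | 83/82 = 101.2% | 110/109 = 100.9% |
| Last dose of Days 7, 14, 21 at home (−3) | 28/28 = 100% | 52/55 = 94.5% | 79/82 = 96.3% | 106/109 = 97.2% |
| Both of the above (−3 + 1) | 28/28 = 100% | 53/55 = 96.4% | 80/82 = 97.6% | 107/109 = 98.2% |
| Last dose of Days 2, 7, 14, 21 at home (−4) | 28/28 = 100% | 51/55 = 92.7% | 78/82 = 95.1% | 105/109 = 96.3% |

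**Effect on a real missed dose (BID, true value 54/55 = 98.2%).** With the Day 26 double count, the score is (55 − 1 + 1)/55 = 100%, and the missed dose disappears. If the missed dose is the one due after leaving on one visit day, and it is recorded as missed, it is subtracted without ever having been added: (55 − 1 − 1)/55 = 96.4%.

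**Cohort A, separate issue.** If the sum over all forms is taken literally, the single-dose-period drop enters the numerator but not the denominator: (28 + 1)/28 = 103.6%. This does not depend on where MDTP doses were taken.

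**The case against.** The formula gives exactly 100% under a pattern that fits the protocol well. Subjects stay until after the evening assessments on Days 7, 14 and 21, and SAP 12.4 schedules IOP to 12 hours on those days. Staff dose subjects while they are on site, and Day 26 is listed as an outpatient dosing day. If sites work that way, neither error arises. This stands, and it is why the figures are possible rather than expected values. It does not remove the defect: evening admission on Day 26 together with staff dosing on site leaves an in-unit dose open, and no text requires the last dose of a visit day to precede departure.

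Three stronger readings are tempting and are not supported.

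- A reader might infer one range of about 93% to 104% driven by dosing location. Location never moves the QD score, and 103.6% comes only from reading the form count against the section's MDTP-only scope. No cohort spans that range on the planned schedule.
- A reader might take 92.7% as the natural low end. It needs a home dose on Day 2, whereas Protocol 7.1.2.2 starts outpatient dosing on Day 3.
- A reader might infer that compliance is the only evidence of dosing and is used to interpret a weak IOP response. SAP 9.1 also summarizes total drops and treatment duration and lists doses received. The analysis sets in SAP 4.3 to 4.5 and the PD analyses in SAP 12.4 to 12.6 do not use compliance.

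**Conclusion.** The rule is incomplete as written. For BID, TID and QID completers with perfect dosing, the score can exceed 100% by one dose (0.9 to 1.8 points) if the last Day 26 dose is given in the unit. It can fall short by three doses (2.8 to 5.5 points) if the last dose on Days 7, 14 and 21 is taken at home; a split Day 2 would cost one dose more. The size rests on site practice and CRF instructions that the documents do not show, and on one form entry per dosing occasion.

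The Cohort A point is a wording conflict within SAP 9.2. The MDTP-only scope is the natural reading, but the form count does not repeat it.

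Compliance is a descriptive summary and defines no analysis set, so this is a desirable clarification and does not threaten the study's conclusions. It concerns completers only; the rule for subjects who stop early is a different matter.

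**What to change.** Amend SAP 9.2 in two places.

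1. State that only MDTP instillation forms are summed, so the single-dose-period drop is excluded.
2. For completers, replace the date-difference term by a count in which each scheduled dose enters once. For example: actual doses = 27x + 1, minus missed home doses on the accountability CRF, minus scheduled on-site doses with no instillation record. Say that a visit-day dose taken after leaving, or before check-in on Day 26, belongs to the home part.

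The last subtraction is needed. The present formula lowers compliance when a clinic dose is omitted, and expected minus accountability-recorded missed doses would lose that. Under this rule an adherent completer scores 28/28, 55/55, 82/82 or 109/109 wherever doses were taken.

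Counting doses from the diaries is an alternative, but Protocol 10.2.3.2 lists diaries as source data, and Protocol 6.5 specifies eCRF capture only for in-clinic dosing details, so diary times may not be in the database.

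The cost is a small SAP edit and a small programming change. The downside is reliance on the recorded missed-dose count, which the present formula already has.

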4.5 Discontinuation of Subjects

A subject may withdraw from the study at any time for any reason without prejudice to their future medical care by the physician or at the institution. The investigator or sponsor may withdraw the subject at any time (eg, in the interest of subject safety). The investigator is encouraged to discuss withdrawal of a subject from investigational product with the medical monitor when possible.

If investigational product is discontinued, regardless of the reason, the early withdrawal evaluations listed in Table 1 are to be performed as completely as possible. Whenever possible, all discontinued subjects should also undergo the protocol-specified follow-up. Comments (spontaneous or elicited) or complaints made by the subject must be recorded in the source documents. The reason for termination and date of stopping investigational product must be recorded in the electronic case report form (eCRF) and source documents.

Randomized subjects who discontinue from the study may be replaced at the sponsor's discretion to ensure that at least 6 out of 7 subjects complete a dosing regimen cohort. Replacement subjects will be assigned to the same treatment group as the subject they are replacing.

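### SAP 9.2 ends expected doses at treatment discontinuation but counts actual doses to the study-termination date, so compliance is inflated for early stoppers whenever the second date is later

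*SAP*

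**What the plan says.** SAP 9.2 defines compliance as actual doses over expected doses, times 100, for the multiple-dose period only ("Treatment compliance will be calculated for MDTP only and will be calculated as"). With x doses per day:

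- **Expected doses, completer:** 27x + 1, because "the last dose was taken on the morning of Day 28".
- **Expected doses, early stopper:** "If the subject discontinued the treatment, the date of treatment discontinuation will be used for date of expected last dose". The count is x × (that date − first-dose date + 1).
- **Actual doses:** instillations recorded in clinic, plus, for each interval between visits, x × (last-dose date before check-in − date of the previous clinic instillation) − missed doses. The last-dose date normally comes from the accountability form completed at the visit.
- **Actual doses, early terminator:** "If a subject has terminated the study early, the date of early termination on the Study Completion 1 CRF will be used".

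The documents keep stopping drug and leaving the study apart. SAP 5 tabulates the two as separate disposition categories. Protocol 4.5 adds that "Whenever possible, all discontinued subjects should also undergo the protocol-specified follow-up", and that "The reason for termination and date of stopping investigational product must be recorded in the electronic case report form (eCRF) and source documents". The drug-stop date is therefore collected in its own right.

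**The concern.** The two halves of the ratio have different cut-offs. The denominator stops on the day treatment is discontinued. The numerator runs to the day the subject is recorded as having terminated the study. Any day between the two is credited as fully dosed, although no dose was taken or due. The missed-dose term removes this credit only if sites enter the untaken doses after the stop as missed, and SAP 9.2 has no rule telling them to.

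Safety and tolerability are the primary objective, and subjects who stop early are the ones whose dosing a reader will look at most closely. The rule can present them as over-compliant and offset doses they really did miss. It also sits badly with the rest of the SAP. Section 9.1 ends treatment duration at the last dose taken, and section 15.2 falls back on a visit date only when the last-dose date is missing. Section 9.2 substitutes the termination date even when the last-dose date is known.

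**Working it through.** **Inputs.** The formula is from SAP 9.2. Visit days are from the schedule of events (Days 1, 2, 7, 14, 21, readmission on Day 26, then Days 27 and 28). The documents give no typical S or T, so these are assumptions. I also assume that all doses on visit days are given in clinic.

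**Completer, twice daily (x = 2).** Days 1 and 2 in clinic, 4; home to Day 6, 2 × (6 − 2) = 8; Day 7, 2; home to Day 13, 2 × (13 − 7) = 12; Day 14, 2; home to Day 20, 2 × (20 − 14) = 12; Day 21, 2; home to Day 26, 2 × (26 − 21) = 10; Day 27, 2; Day 28, 1. The total is 55, which equals 27 × 2 + 1. The same count gives 28, 82 and 109 for x = 1, 3 and 4, again equal to 27x + 1. The formula is sound for completers.

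**Early stopper, general form.** With m doses entered as missed, actual = xT − m and expected = xS. Reported compliance = 100 × (T − m/x)/S. With m = 0 this is 100 × T/S, a relative inflation of (T − S)/S that does not depend on x.

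**Twice daily, S = 10, T = 14, all 20 doses taken.** Days 1 and 2, 4; home to Day 6, 8; Day 7, 2; subtotal 14. Final interval, 2 × (14 − 7) = 14. Actual = 28, expected = 2 × 10 = 20, reported 140%. The true value is 20/20 = 100%.

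**Range over assumed gaps, no post-stop doses entered as missed:**

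| Stop day S | T = S | T = S + 1 | T = S + 3 | T = S + 7 |
|---|---|---|---|---|
| 5 | 100% | 120% | 160% | 240% |
| 10 | 100% | 110% | 130% | 170% |
| 18 | 100% | 105.6% | 116.7% | 138.9% |

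For a stop on Day 25 a one-day gap gives 26/25 = 104%.

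**Masking.** Same twice-daily subject, with 5 of the 20 doses missed and recorded. True compliance is 15/20 = 75%. Reported is (28 − 5)/20 = 115%.

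**Cancellation.** If the 2 × (14 − 10) = 8 untaken doses after the stop are entered as missed, the adherent subject scores (28 − 8)/20 = 100%.

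**Group mean.** Four subjects at 100% and one at 140%: (400 + 140)/5 = 108%.

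**The case against.** The strongest reply is that the gap may seldom arise. The Study Completion 1 form is not described in either document. SAP 5 says reasons for leaving the treatment period come from the eCRF termination page, so one event may supply both dates. Several protocol rules (4.5.1, 6.2.3.2, 6.2.4, 8.1.7) take the subject out of the study itself, and Protocol 7.1.3 describes follow-up as coming after such a discontinuation. The follow-up request in Protocol 4.5 therefore does not prove that the termination date falls later. Missed doses are also left undefined, so sites may enter untaken doses after the stop and cancel the error.

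This stands as a limit on frequency and size. It does not rescue the rule, which gives the right answer only if the two dates coincide or an unwritten data-entry convention is followed.

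The consequences are also bounded. SAP 9.1 separately summarizes total drops and treatment duration to the last dose taken, and individual compliance is listed, so an odd value can be checked. Compliance does not define the safety, PK or PD set and enters no PK or PD analysis. SAP 16 lists exposure outputs but no table titled for compliance. All of this holds.

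**Conclusion.** The mismatch is in the text of SAP 9.2 and should be corrected. When T is later than S and post-stop doses are not entered as missed, an otherwise adherent early stopper is reported at 100 × T/S, and recorded non-compliance can be offset. When T equals S, or every untaken dose is entered as missed, nothing is wrong. The effect stops at the descriptive compliance summary and listing.

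Three stronger readings are not supported:

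- A reader might infer that early stoppers will generally show compliance far above 100%. That needs a gap that is long relative to time on drug, and the documents do not show how long gaps are. A one-day gap gives 104% to 120% for stops between Day 25 and Day 5.
- A reader might take the Day 88 visit as the termination date and obtain an extreme percentage. Protocol 3.2 and 9.5 make that visit the planned study completion, so a subject who attends it has not clearly terminated early.
- A reader might expect the worst distortion in a placebo group of two. SAP 4.3 pools placebo subjects for safety analyses, and SAP 11 pools them by regimen for the multiple-dose ocular summaries. The SAP specifies no placebo summary group of two.

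**What to change.** In SAP 9.2, delete the substitution of the early termination date in the actual-dose count. Use instead the recorded date of the last dose actually taken, from the Study Drug Accountability CRF or the eCRF date of stopping investigational product, and never later than the treatment discontinuation date. State that only missed doses up to that date are subtracted, so that later untaken doses are not removed twice.

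Leave the denominator as it is ("the date of treatment discontinuation will be used for date of expected last dose"). Using the last-dose date there as well would hide a subject who quietly stopped before being formally discontinued. On twice-daily dosing, with the last dose on Day 10 and discontinuation on Day 20, it would give 20/20 = 100%. The existing denominator gives 20/40 = 50%.

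Under the change, the adherent Day 10 stopper scores (14 + 2 × (10 − 7))/20 = 20/20 = 100%, and the subject with five missed doses scores 15/20 = 75%. The cost is a sentence or two in the SAP and the matching programming. Protocol 4.5 already requires the stop date, so no new data are needed.
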